Smokeless tobacco	Also called chew, dip, or snuff, this tobacco product is chewed rather than smoked.	SLT
Adverse event	Any mild reaction to the product including a headache, trouble sleeping, dizziness, or nausea.	AE
Serious adverse event	A serious reaction or breach in confidentiality.	SAE
Center for Tobacco Research	The Center for Tobacco Research provides evidence-based knowledge surrounding the regulation of tobacco products to inform individual health decisions as well as public health regulations.	CTR
Inclusion/Exclusion	Criteria that the participant must meet or not meet in order to be considered for the study.	I/E
Early Termination	When the participant is removed from the study at the discretion of the PI.	ET

Introduction

Abstract

Nicotine pouches are novel smokeless tobacco products that are marketed as substitutes for cigarettes and gaining in popularity. They may have high appeal in Ohio Appalachia, a region with high prevalence of smoking and a population disparately impacted by tobacco-associated cancer. There is little research on the abuse liability of nicotine pouches (i.e., the likelihood of sustained patterns self-administration) in Ohio Appalachia to understand their appeal and potential impact on public health and tobacco-related disparities. This study is designed to estimate the abuse liability of nicotine pouches with varying nicotine concentrations relative to cigarette smoking in a clinical study with Appalachian smokers. This pilot will provide the foundation for a line of research that can inform policy locally and nationally. Dissemination of

our results through community partners will inform efforts to reduce tobacco-associated cancer disparities in Ohio Appalachia.

Background

Tobacco use is a public health threat in the United States (U.S.),¹² particularly in Appalachian regions.¹ Declines in the prevalence of tobacco use in Appalachia have not mirrored the rest of the country,¹³ leading to widening disparities in cancer.^{5,6} Reasons for the high prevalence of tobacco use in Appalachia include social norms supporting tobacco use in the home;¹⁴ viewing tobacco use as a rite of passage;² a history of economic reliance on tobacco farming;¹⁴ promotion of smokeless tobacco (SLT) use in situations when cigarette smoking is unsafe (e.g., coal mining);¹⁵ and marketing that reinforces Appalachian cultural values of individuality and ruggedness.^{2,16}

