Aim 2: Participants will be invited to the CTR to complete study procedures. At visit 1, informed consent will be collected. During visits 1-3, participants will complete an eCO test, take a pregnancy test if applicable, a line will be placed for IV blood draw by the staff research nurse for IV blood draws throughout the course of the study visit, and be asked to either try a 3mg NP or a synthetic NP and then sit in the room for 60 minutes. Participants will be asked a series of 3 questionnaires before, during, and after each product is used. Blood draws will be collected from the line at 0 5, 15, 30, 60, and 90-minutes. 3mLs, or a little less than 1 teaspoon, of blood will be drawn at each timepoint.

Measures of craving and withdrawal relief will be assessed at each blood draw (see attached surveys). If a collection interval is not met there will be no draw retroactively. Participants will be assessed for AE throughout procedures and prior to leaving the visit.

Inclusion/Exclusion Criteria

Aim 1: Adults aged 21 and older who reside in an Ohio Appalachian county and smoke at least 5 cigarettes per day will be considered for this project. Smokers who use other tobacco products (e.g., SLT, electronic cigarettes) > 10 days a month will be ineligible because our goal is to characterize the abuse liability of NPs among those who exclusively or primarily smoke cigarettes.

Inclusion	Exclusion
Age 21 years or older	Use tobacco products other than cigarettes >10 days per month.
Reside in an Ohio Appalachian county or surrounding rural area	Use NP in the past 3 months
Willing to complete study procedures, including abstaining from all tobacco,	Unstable or significant psychiatric conditions (past and stable conditions will be allowed)

nicotine, and marijuana for 12 hours before clinic visits	
Ability to read and speak English	Pregnant, planning to become pregnant, or breastfeeding
Smoke at least 5 cigarettes per day for the past 30 days	History of cardiac event or distress within the past 3 months
	Currently attempting to quit all tobacco use
	Self-reported diagnosis of lung disease including asthma (if uncontrolled or worse than usual), cystic fibrosis, or chronic obstructive pulmonary disease

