Participants will need to abstain from tobacco and nicotine products for ≥ 12 hours prior to their study visit. To check for abstinence from tobacco, participants will perform exhaled carbon monoxide testing ($eCO < 10\text{ppm}$) and confirm via self-report that they have not used any other nicotine products over the last 12 hours.

Pregnancy Test

All subjects capable of becoming pregnant will need to take and produce a negative pregnancy test in order to proceed further.

Pre-intervention questionnaire to be administered

This questionnaire will assess sociodemographics, tobacco use history, NP use history, and nicotine dependence. These questionnaires will be administered during Visit 1.

IV line insertion

Because blood draws will occur at set intervals, an IV line will be inserted by a trained staff nurse.

Blood draw to obtain baseline plasma nicotine levels

Next, participants will be reminded that in addition to the exhaled CO test, their abstinence will be confirmed at the time of visit via blood plasma nicotine analysis. 3 mL venous blood sample will be collected for later analysis to confirm abstinence. This blood draw will also be used to establish baseline plasma nicotine levels to estimate total nicotine delivery.

Administer intervention

Aim 1: The participant will receive a 3mg NP, 6mg NP, or be asked to smoke one cigarette of their usual brand depending on the randomization assignment. If smoking a cigarette, participants will be asked to smoke one cigarette following a standardized puffing protocol: they will take one puff every 30 seconds for 5 minutes. If using an NP, participants will be asked to place the pouch between their upper lip and gum and leave it in place for 30 minutes.

Aim 2: The participant will receive a 3mg tobacco-derived NP or a 3mg synthetic NP on randomization assignment. Participants will be asked to place the pouch between their upper lip and gum and leave it in place for 30 minutes.

Peri-intervention questionnaire to be administered

The QSU and MNWS surveys will be administered while at each blood draw interval of 0, 5, 15, 30, 60, and 90 minutes.

Post-intervention questionnaire to be administered

Measures of product appeal and behavioral intentions will be assessed after the participant has the cigarette or NP (Aim 1) or the tobacco-derived vs. synthetic NP (Aim 2).

Schedule return visit and provide gift card for participation

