Schedule return visit per subject and interviewer availability that is >2 days after the current visit. Provide \$100 via Clincard for their participation out of the up to \$350 possible. If it is their last visit has been completed within 1 month from consent, they will receive \$150 during their last visit.

Post-Enrollment Survey

6 months after enrolling, participants from Aims 1 and 2 will be recontacted via phone, text, and email for the opportunity to participate in a short online REDCap survey. Participants will complete a short consent addendum and respond to survey questions regarding their current tobacco product use and opinions surrounding nicotine pouches. For their time, they will receive a \$10 Amazon gift code.

Procedure Manual

Study procedures, including conducting pregnancy tests, blood draws, blood processing and analysis, gift card administration, and other procedures will be thoroughly explained in the study procedure manual.

4. Study Administration

Randomization, Blinding, and Unblinding

Participants will be randomized within the secure database, REDCap. The randomization piece involves at which of the 3 visits they are to use each product (Aim 1: 3mg NP, 6mg NP, or their own usual brand cigarette and Aim 2: the tobacco-derived 3mg tobacco-derived NP or the 3mg synthetic pouches). Participants will be blinded during study visits and at the end of their third visit will be informed which product they had at each visit.

Study Timelines, Number of Sites, and Enrollment

Participant Timeline

There will be a total of 3 study visits and 1 online survey opportunity 6 months after the completion of the final study visit. The study timeline for each participant will vary. Clinic visits can be completed in as little as a week and a half or as long as 2 months, but will ideally be completed within 3 week's timeframe for retention and administrative purposes. The study visits will take approximately 3 hours each. The online survey will take approximately 10 minutes to complete and will be offered 6 months after completing the final visit.

Duration of Study

We anticipate the clinical trial to take six months to complete. After that, we anticipate that it will take 1-1.5 years to clean and analyze data and disseminate results.

Total Number of Study Sites

All recruitment and enrollment activities will be completed within the CTR.

Total Number of Subjects Projected

55 subjects will be enrolled and each subject must meet I/E criteria.

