All adverse events will be reported to the OSU IRB. We will monitor for risks associated with smoking and nicotine pouch use by screening participants for general medical precautions (pregnancy, cardiovascular disease). Any adverse events, breaks of confidentiality, or any other data or safety issues that arise will be discussed immediately between study personnel and [name]. [name] will be responsible for completing an Adverse Events Form should an event occur. [name] will report potential unanticipated problems involving risks to subjects or others (UPIRSOs) to the OSU IRB within 24 hours of having received notice of the event. [name] will gather any information needed to investigate the event and to determine subsequent action. Any subsequent action will be documented and reported to the OSU IRB and the Program Officer at NIH. Adverse event reports will be reviewed annually with the OSU IRB to ensure participant safety.

Risks and Benefits to Participation

Risk Assessment

Every attempt will be made to reduce risk to the participant. The research protocol calls for current smokers who do not plan to quit smoking to try a NP at 3mg or 6mg or smoke their regular cigarette brand (Aim 1) or try a 3mg tobacco-derived NP or 3mg synthetic NP (Aim 2) during a supervised study visit. NPs are no more harmful than conventional cigarettes, and there is some evidence that they may offer reduced harm. Questionnaires and exhaled breath collection procedures are all non-invasive and involve minimal risk to study participants. Potential risks are as follows: a) risk of using NPs, b) use of cigarettes (Aim 1 only), c) loss of confidentiality or privacy, d) potential for undermining smoking cessation, and e) slight risk of discomfort, bruising and infection with blood draw.

Potential Benefits of Trial Participation

Participants are not expected to directly gain any benefits from this study. Participants may indirectly consider quitting tobacco products or choosing a harm reduction product as a result of their involvement with this investigation though this is not a study objective. Through their contributions to science, subjects provide insight into a novel tobacco product that has potential to reduce or increase the harm of tobacco use in Appalachia (Aim 1) or Ohio in general. Moreover, data collected will inform public health efforts, policy, and clinical care aimed at reducing tobacco-related disparities in Appalachia.

Risk-Benefit Assessment

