2. Loss of Confidentiality and Privacy: Confidentiality will be maintained by numerically coding all data, disguising identifying information, and keeping data locked in file drawers or in a secure, password protected database. All biospecimen samples are kept in a locked freezer and also will be deidentified. Names of participants will be kept separate from participant data. Only study research personnel and the PI will have the information that connects participants' names and ID numbers. All electronic data will be numerically coded and stored in a password-protected database, on a password-protected computer in a secure research space. Participant information will be accessible only to research staff, who are pledged to confidentiality and have completed training in the ethical conduct of research (i.e., both HIPAA and CITI trainings). Identifying information will not be reported in any publication.
3. Potential for Undermining Cessation: The study sample is comprised of smokers with no plan to quit in the next three months. Therefore, we are not asking smokers who want to quit to continue smoking. The PI will be available for any questions that participants may have about NPs, smoking, or smoking cessation. It is important to note that the use of NPs incurs no greater harm than if the participant decided on

his/her own to use the product. Among those screened and ineligible/uninterested, referral resources for smoking cessation will be provided for those who inquire.

Among study participants, information on cessation resources will be provided at the final visit and if at any time during the study participants are interested in smoking cessation services, a list of smoking cessation resources will be provided.

4. Slight risk of bruising, discomfort and infection with blood draw: Blood will be collected by trained research staff. Sterile instruments will be used and for blood draws, the participants skin will be cleaned with an alcohol wipe at the venipuncture site.

6. References

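### The risk section says participants have no plan to quit within three months, but the eligibility tables exclude only a current attempt to quit all tobacco

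*Combined protocol and SAP*

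**What the plan says.** Section 5 describes the sample twice in terms of quit intentions. Under Risk Assessment: "The research protocol calls for current smokers who do not plan to quit smoking". Under Potential for Undermining Cessation, with a time window: "The study sample is comprised of smokers with no plan to quit in the next three months". The next sentence draws the protective conclusion: "Therefore, we are not asking smokers who want to quit to continue smoking".

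Entry is governed elsewhere. The definitions table at the front describes inclusion/exclusion criteria as "Criteria that the participant must meet or not meet in order to be considered for the study", and section 4, Total Number of Subjects Projected, states that "55 subjects will be enrolled and each subject must meet I/E criteria".

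In section 2, Inclusion/Exclusion Criteria, the Aim 1 and Aim 2 tables carry the same single item on quitting, an exclusion: "Currently attempting to quit all tobacco use". The smoking criterion, also the same in both, is "Smoke at least 5 cigarettes per day for the past 30 days".

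**The concern.** The risk section presents the absence of quit plans as a fact about the sample and makes it the first answer to the possibility that the study undermines cessation. A fact of that kind has to come from an entry criterion, and none supplies it. A current attempt and a plan are different states: someone can plan to stop next month while making no attempt today.

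At stake is the accuracy of a participant-protection statement. An ethics board reading section 5 would take it that smokers intending to quit soon are kept out, whereas staff applying the tables would have no written ground to turn them away. The description of the study population in any later report could be wrong in the same way.

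**Working it through.** No power or sample-size figure is involved, so the check is mainly a comparison of text.

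**1. What each place requires**

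| Place | Condition on quitting | Time frame | Scope |
|---|---|---|---|
| Section 5, Risk Assessment | No plan to quit | None given | Smoking |
| Section 5, Potential for Undermining Cessation | No plan to quit | Next three months | Product not named |
| Section 2, Aim 1 table | No current attempt | Present | All tobacco |
| Section 2, Aim 2 table | No current attempt | Present | All tobacco |

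The two statements in section 5 are compatible with each other; one simply adds a window. The mismatch is between them and the tables.

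**2. Whether another criterion fills the gap**

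- The cigarettes-per-day criterion looks back 30 days and is silent on plans.
- Two exclusions in each table use a three-month period, but they concern past pouch use and past cardiac events.
- The paragraph above each table deals with age, residence, cigarettes per day and use of other tobacco products, not with quit plans.
- Section 2, Screening and scheduling phase, lists the screener topics as tobacco use, health status, willingness to travel, demographics and contact details. Quit plans are not named.

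**3. Whether a current attempt can be read to include a plan**

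The tables point the other way. The pregnancy exclusion in each covers both being pregnant and planning to become so. Where the authors meant a plan, they wrote it. The quit item has no such wording.

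**4. Test case**

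Take a smoker of 10 cigarettes a day who meets every other criterion, intends to stop in four weeks and has not started. This person meets the smoking criterion and does not trigger the quit exclusion, so the tables admit them. They do not fit either description in section 5.

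There is a second, narrower gap. The table item concerns quitting all tobacco, so someone trying to give up cigarettes alone is not clearly excluded, although Risk Assessment speaks of smoking.

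**5. Size of the exposure**

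- Study cigarettes: in one of the three Aim 1 visits the participant will "be asked to smoke one cigarette of their usual brand depending on the randomization assignment". With N = 40, that is 40 × 1 = 40 at most. Aim 2 has no cigarette visit, so 0.
- Overlap in time: three months is about 13 weeks. Section 4, Participant Timeline, gives a clinic phase of 1.5 weeks at the shortest, ideally 3 weeks, and 2 months at the longest. These are 1.5/13 = 12%, 3/13 = 23% and 2/3 = 67% of the window. Visits could therefore coincide with or precede a planned quit date inside the window. These ratios show overlap only; they do not measure how many people are affected or any harm to them.

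**The case against.** The strongest reply is that this is a wording difference with little consequence. The group most directly exposed, smokers already trying to quit, is excluded. Aim 1 adds one supervised cigarette for people who already smoke at least five a day, and Aim 2 adds none. Section 5 separately provides cessation resources at the final visit, a resource list on request at any time, and access to the principal investigator. The Preliminary Research section reports lower interest in cessation among Appalachian tobacco users than among others, which suggests a smaller affected group in Aim 1. All of this stands, and it is why the practical risk is rated small. The Appalachian comparison, however, gives no absolute level of quit plans and does not cover Aim 2, which recruits across Ohio.

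A second reply is that the condition is misplaced rather than absent: Risk Assessment is itself a written statement of who is sought, and the unseen screener may ask. That is possible, and it limits what can be said about the people actually enrolled. It does not rescue the text. Enrolment is tied to the inclusion/exclusion criteria, and even if the screener asks, no written criterion makes a plan to quit disqualifying.

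**Conclusion.** The concern holds. As written, the entry rules admit smokers who plan to quit within three months, and the risk section says there are none. The inference that follows in section 5 is unsupported to the same extent.

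This should be corrected, but it does not threaten the analysis: no effect on power, sample size or the within-subject product contrasts is claimed. The size in participants is unknown because the documents give no figure for quit plans. The conclusion rests on reading the eligibility tables as the operative entry criteria, as the definitions table and section 4 indicate, and on the absence of a quit-plan criterion anywhere else in the documents. It makes no claim that the enrolled sample in fact differs from the description, since the screener is not available.

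**What to change.** Reconcile the two eligibility tables in section 2 with Risk Assessment and Potential for Undermining Cessation in section 5. Either route would do, and which entry rule to adopt is for the investigators to decide.

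- **Bring the tables into line with the risk section.** Carry the protocol's own no-plan condition into both tables, with one stated time frame and a clear scope (smoking or all tobacco), and into the screener if it is not there already. Cost: one line per table, possibly one screener item, and an ethics-board amendment. Recruitment might slow slightly; the documents give no figure for this.
- **Bring the risk section into line with the tables.** Remove the no-plan statements and the inference drawn from them, and describe the sample by the exclusion actually applied. Cost: text edits in two places. The section would then rest on that exclusion, the cessation resources and access to the principal investigator. The right to withdraw could be cross-referenced from Informed consent (section 3) and Subject Completion, Withdrawal, and Early Termination (section 4), where it now appears.
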